**- Protocol Revision Record -**

**Original Protocol:** 10/13/16

[figure not shown]
Amendment #1:	07/17/2017
Amendment #2:	08/15/2017
Amendment #3:	01/09/2018
Amendment #4:	11/26/2019
Amendment #5:	04/08/2020
Amendment #6:	11/04/2021

## SCHEMA

## PROTOCOL SYNOPSIS

Sponsor	Vanderbilt-Ingram Cancer Center
Protocol Title	A phase Ib trial of fulvestrant, palbociclib (a CDK4/6 inhibitor) and erdafitinib (JNJ-42756493, a pan-FGFR tyrosine kinase inhibitor) in ER+/HER2-/FGFR-amplified metastatic breast cancer (MBC)
Protocol Number	VICCBRE16126 (NCT03238196)
Phase of Development	Phase Ib
Investigational Product and Mechanism	
 
Erdafitinib, an oral pan-FGFR inhibitor (please note that the combination of erdafitinib, palbociclib and fulvestrant is also investigational)
 

Non-Investigational Products and Mechanism	
 
Palbociclib, a CDK4/6 inhibitor
 
Fulvestrant, a selective estrogen-receptor downregulator (SERD)
 

Treatment Schedule Dose/Route	
 
Erdafitinib (4 – 8 mg) mg PO daily
 
Palbociclib 125 mg PO daily from day 1 – 21, every 28 days
 
Fulvestrant 500 mg IM once every 28 days
 

Objectives	
Primary Objectives
 
 
To determine the safety and tolerability of fulvestrant, palbociclib and erdafitinib in patients with ER+/HER2-/FGFR-amplified MBC.
 
 
Secondary Objectives
 
 
To determine the anti-tumor effect of fulvestrant, palbociclib and erdafitinib in patients with ER+/HER2-/FGFR-amplified MBC.
 
Pharmacokinetic assessments of erdafitinib
 
 
Correlative Objectives
 
 
To determine the therapeutic predictive role of FGFR1-4, CCND1-2, CDK4 and CDK6 amplifications, and RB1 and ESR1 mutations on clinical outcome
 
To determine if the FGFR1 amplification levels by FISH and cfDNA is an early surrogate of response
 
To determine if the cfDNA results at disease progression show new genomic alterations potentially associated with resistance to CDK4/6 and FGFR inhibition
 
To determine pharmacodynamic biomarkers of FGFR inhibition
 

Endpoints	
Primary Endpoint
 
 
Assessment of DLT during the first 4 weeks of treatment (cycle 1)
 
Determination of MTD
 
 
Secondary Endpoints
 
 
Progression Free-Survival (PFS)
 
Overall response rate (ORR)
 
Clinical benefit rate (CBR; complete response + partial response + stable disease without disease progression at 6 months)
 
Pharmacokinetic assessments of erdafitinib
 
 
Correlative Endpoints

	

• FGFR1 fluorescence in situ hybridization (FISH)

• Next Generation Sequencing (NGS) of baseline or archival tumor specimen

• Plasma tumor cell free [cf] DNA at baseline, at 4 weeks and at disease progression

• Serial measurements of serum phosphate, calcium, vitamin D, parathyroid hormone (PTH), FGF23, sFGFR2, sFGFR3 and sFGFR4

Trial Design	This is an open-label, multi-institution, phase Ib trial that evaluates the safety, tolerability, and anti-tumor activity of fulvestrant, palbociclib with erdafitinib in patients with ER+/HER2-/FGFR-amplified metastatic breast cancer (MBC).
Number of Patients	

• Minimum: 26 patients

• Maximum: 35 patients

Participating Institutions	

• Vanderbilt-Ingram Cancer Center (Coordinating Center)

• TBCRC (4 centers)

Duration of Therapy	In the absence of treatment delays due to adverse events, treatment will continue until: 

• Disease progression

• Inter-current illness that prevents further administration of treatment

• Unacceptable adverse event(s)

• Patients decides to withdraw from the study

• Significant patient non-compliance with protocol

Duration of Follow-up	

• Patients will be followed every three months until disease progression, or until death from any cause (whichever occurs first)

• Patients removed from study for unacceptable treatment related adverse event(s) will be followed until resolution or stabilization of all treatment related adverse events to Grade 2 or lower

• Patients continuing fulvestrant who have discontinued erdafitinib or palbociclib for any reason other than disease progression will be followed until disease progression

Patient Selection	
Inclusion Criteria (abbreviated)
 

• Patients (female or male) must provide informed written consent and must complete all screening assessments as outlined in the protocol

• Patients must be able to swallow and retain oral medication

• Patients must be <math>\geq 18</math> years of age

• Female patients of no childbearing potential.

 
Patients must be post-menopausal by at least one of the following criteria prior to enrollment:
 

○ Subjects at least 60 years of age; OR

○ Subjects under 60 years of age and naturally (spontaneous, no alternative pathologic or physiological cause) amenorrhea for at least 12 months; OR

○ Medical ovarian failure confirmed by follicle-stimulating hormone (FSH) and estradiol levels in the post menopausal range per local institutional normal range; OR

○ Prior bilateral oophorectomy; OR

○ Prior radiation castration with amenorrhea for at least 6 months; OR

○ Treatment with a luteinizing hormone-releasing hormone (LH-RH) agonist (such as goserelin acetate or leuprolide acetate) is permitted for induction of ovarian suppression as long as it has been initiated at least 28 days prior to study enrollment

 

• ECOG performance status 0 - 1

• Clinical stage IV or inoperable locoregional recurrent invasive mammary carcinoma that is:

○ ER+ and/or PgR+ (<math>\geq 1\%</math> positive stained cells) by immunohistochemistry (IHC)

○ HER2-negative (by IHC or FISH, per ASCO guidelines)

○ FGFR1 - 4amplified (may be determined by local assessment through either targeted capture next generation sequencing (NGS), plasma tumor cell free [cf] DNA or FISH) in 50% of the patients

--------------------------	---

	
participating in the expansion cohort of the trial (not necessary in the escalation cohort)
 

○ Evaluable (may have either measurable or non-measurable disease)

● Patients must have available tissue (archival formalin-fixed paraffin embedded (FFPE) blocks or fresh frozen biopsy from primary tumor or metastatic tumor biopsy) for correlative studies. Tissue source needs to be located and available at the time of registration (tissue needs to be submitted within 3 weeks of study initiation). Patients will not be able to start study drugs without tissue availability. Submission of tissue can be waived, if approved by the Study Chair in case of extraordinary/catastrophic circumstances.

● Current use of any of the drugs listed on the Cautionary Concomitant Medications list has to be approved by the Study Chair

● Patient must have had at least one line of therapy in the metastatic setting

● Patients must have adequate hematologic, hepatic, and renal function. All laboratory tests must be obtained within 2 weeks from study entry. These include:

○ ANC <math>\geq</math> 1,500/mm^3

○ Platelet count <math>\geq</math> 100,000/mm^3

○ HgB <math>\geq</math> 9.0 g/dL

○ Creatinine clearance <math>\geq</math> 40 mL/min/1.73 m^2

○ SGOT, SGPT <math>\leq</math> 2.5 x ULN if no liver metastasis present

○ SGOT, SGPT <math>\leq</math> 4 x ULN if liver metastasis present

○ Albumin <math>\geq</math> 2.0 g/dL

○ Total serum bilirubin <math>\leq</math> 1.5 x ULN (<math>\leq</math> 3 x ULN or direct bilirubin <math>\leq</math> 1.5 x ULN if known Gilbert's syndrome)

○ Potassium within institutional normal limits

○ Phosphorus <math>\leq</math> institutional upper limit of normal

 
Exclusion Criteria (abbreviated)
 

● Prior use of an FGFR inhibitor

● More than 2 lines of chemotherapy in the metastatic setting. There is no limit on endocrine therapy lines

--	--

	

• Radiation therapy <math>\leq</math> 2 weeks prior to study entry. Patients who have received prior radiotherapy must have recovered from toxicity (<math>\leq</math> grade 1) induced by this treatment (except for alopecia)

• Prior cancer therapy (except for endocrine therapy) must have been discontinued for 1 week prior to initiation of study drugs

• Concurrent anti-cancer therapy other than the ones specified in the protocol is not permitted during study participation. Bisphosphonates or denosumab are allowed

• Major surgery within 4 weeks of enrollment

• Herbal preparations are not allowed throughout the study, and must be discontinued at least 14 days prior to initiation of study treatment

• Any corneal or retinal abnormality likely to increase the risk of eye toxicity, such as:

○ Current corneal pathology such as keratitis, keratoconjunctivitis, keratopathy, corneal abrasion, inflammation or ulceration

○ Uncontrolled glaucoma despite standard of care therapy

○ Diabetic retinopathy with macular edema

○ Known active wet, age-related macular degeneration (AMD)

○ Known central serous retinopathy (CSR) or retinal vascular occlusion (RVO)

• Uncontrolled intercurrent illness including, but not limited to:

○ Malabsorption syndrome significantly affecting gastrointestinal function

○ Ongoing or active infection requiring antibiotics/ antivirals

○ Impairment of lung function (COPD <math>></math> grade 2, lung conditions requiring oxygen therapy)

○ Symptomatic congestive heart failure (class III or IV of the New York Heart Association classification for heart disease)

○ Unstable angina pectoris, angioplasty, stenting, or myocardial infarction within 6 months

○ Clinically significant cardiac arrhythmia (multifocal premature ventricular contractions, bigeminy, trigeminy, ventricular tachycardia that is symptomatic or requires treatment [National Cancer Institute -

--	--

	
Common Terminology Criteria for Adverse Events, Version 4.03, grade 3]
 

○ QTcF <math>\geq</math> 480 msec on screening EKG

○ Known history of QT/QTc prolongation or Torsades de Pointes (TdP)

○ ST depression or elevation of <math>\geq</math> 1.5 mm in 2 or more leads

○ Diarrhea of any cause <math>\geq</math> CTCAE grade 2 that does not resolve within a few days under adequate treatment

○ Psychiatric illness/social situations that would compromise patient safety or limit compliance with study requirements including maintenance of a compliance/pill diary

○ Symptomatic brain metastases (patients with a history of brain metastases must be clinically stable for more than 4 weeks from completion of radiation treatment and off steroids)

○ Known history of chronic liver or renal failure

○ Poor wound healing capacity

Study Assessments	
Safety Assessment:
 

● History, physical exam, and routine blood work such as blood counts and comprehensive metabolic panel will be performed on day 1 of each treatment cycle.

● Analyses will be performed for all patients having received at least one dose of study drugs. The study will use the NCI CTCAE v4.03.

 
Anti-tumor Assessments:
 

● CT scans of the chest, abdomen, and pelvis and bone scan (when applicable) are to be performed approximately every 8 weeks

 
Exploratory Assessments:
 

● Tumor tissue collection: baseline

● Plasma collection: every other month. cfDNA will be performed at baseline, at 4 weeks after treatment initiation (Cycle 2 Day 1), and at disease progression (end-of-treatment)

● Pharmacodynamic studies: Day 1 and 15 of cycles 1 and 2 (for escalation portion only)

● Pharmacokinetic studies: Day 1 and 15 of cycles 1 and 2 (for escalation portion only)

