#### 3.2.1 Palbociclib

Palbociclib is an orally active pyridopyrimidine, first-in-class compound that is a potent and highly selective reversible inhibitor of CDK4/6. Estrogen-activated ER transcription activates cyclin D1 leading to the formation of the cyclin D1-CDK4/6-Rb complex where CDK4/6 phosphorylates and inactivates Rb. Phosphorylated Rb uncouples from E2F transcription factors, which in turn, mediate progression from G1 into S phase of the cell cycle. Thus, by inhibiting CDK4/6, palbociclib prevents tumor cell entry into S phase. Consistent with its CDK4/6 specificity, treatment with palbociclib reduces expression of the proliferation marker Ki67 and is completely inactive in Rb-deficient tumor cells. Preclinical data have shown that endocrine-resistant ER+ breast cancer cells are highly sensitive to the combination of palbociclib with anti-hormonal therapy or palbociclib alone.

Blockade of the ER signaling pathway is synergistic with cell cycle arrest induction, as demonstrated by the more than doubling in median PFS observed in the PALOMA-3 clinical trial. The combination of palbociclib with tamoxifen has also shown synergy *in vitro* against ER+ human breast cancer cell lines. Also, recent data in endocrine resistant models (MCF7-CYP19) indicate a significant benefit of the combination of palbociclib and letrozole as well as palbociclib and fulvestrant over letrozole and fulvestrant alone (Pfizer, Investigational Brochure, Version Dec 2013).

Laboratory studies have shown that human breast cancer cell lines that are more sensitive to palbociclib ( $IC_{50} < 150$  nM) have low levels of CDKN2A (p16) and high levels of Rb1, while resistant cells show the opposite characteristics. Sensitive cell lines were mostly of the luminal ER+ subtype. A phase I trial tested 3 dose levels of palbociclib in patients with solid tumors, enrolling 41 patients at three dose levels, with drug given for 21 days out of every 28 days. The dose limiting toxicity was neutropenia, and the recommended phase II dose was 125 mg. Clinical benefit with objective response was seen in 10/41 (27%) patients for at least 4 cycles, and in 6 patients for at least 10 cycles, one of whom had breast cancer. Other than neutropenia, which was proportionate to drug exposure, palbociclib was well tolerated.

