chemotherapy, but naïve to CDK4/6 inhibitors. Patients received fulvestrant with placebo or with palbociclib. The PFS at time of interim analysis was 9.2 months in the investigational arm vs. 3.8 months for fulvestrant plus placebo arm (HR=0.42; p<0.000001). The most common grade 3 or 4 adverse events in the palbociclib-fulvestrant group were neutropenia (62.0%, vs. 0.6% in the placebo-fulvestrant group), leukopenia (25.2% vs. 0.6%), anemia (2.6% vs. 1.7%), thrombocytopenia (2.3% vs. 0%), and fatigue (2.0% vs. 1.2%). Thirty-three percent of patients had received one line of prior chemotherapy for metastatic disease. Based on these results, in February 2016 palbociclib was FDA-approved in combination with fulvestrant for second line treatment of patients with ER+/HER2-negative MBC.

Of note, the potential for a clinically significant drug-drug interaction between the CDK4/6 inhibitor palbociclib and fulvestrant is very low. A phase III trial has completed accrual, with an initial safety assessment with trough plasma concentrations demonstrating no pharmacokinetic interactions between fulvestrant and palbociclib. *In vitro* data indicate that CYP3A and SULT enzyme SULT2A1 are mainly involved in the metabolism of palbociclib. The strong CYP3A inhibitor itraconazole increased palbociclib AUCinf by approximately 87%, relative to palbociclib given alone. As expected, coadministration of rifampin, a strong CYP3A inducer, decreased palbociclib AUCinf by 85% relative to palbociclib given alone. Palbociclib is a weak time-dependent inhibitor of CYP3A following administration of the clinical 125 mg dose: palbociclib increased the midazolam AUCinf values by 61%, as compared with midazolam alone. *In vitro*, palbociclib is not an inhibitor of CYP1A2, 2A6, 2B6, 2C8, 2C9, 2C19, and 2D6, and is not an inducer of CYP1A2, 2B6, 2C8, and 3A4 at clinically relevant concentrations. *In vitro* evaluations indicated that palbociclib has a low potential to inhibit the activities of drug transporters at clinically relevant concentrations.

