- 4.1.7 Patients must have available tissue [archived formalin-fixed paraffin embedded (FFPE) blocks or fresh frozen biopsy from primary tumor or metastatic tumor biopsy] for correlative studies. Tissue source needs to be located and available at the time of registration (tissue needs to be submitted within 3 weeks of study initiation). Patients will not be able to start study drugs without tissue availability. Submission of tissue can be waived, if approved by the Study Chair in case of extraordinary/ catastrophic circumstances
- 4.1.8 Patients must have had at least one line of systemic therapy in the metastatic setting
- 4.1.9 Current use of any of the drugs listed on the Cautionary Concomitant Med list has to be approved by the Study Chair
- 4.1.10 Patients must have adequate hematologic, hepatic and renal function. All laboratory tests must be obtained within 2 weeks from study drug initiation. These include:
  - a. ANC  $\geq 1,500/\text{mm}^3$
  - b. Platelet count  $\geq 100,000/\text{mm}^3$
  - c. HgB  $\geq 9.0 \text{ g/dL}$
  - d. Creatinine clearance  $\geq 40 \text{ mL/min}/1.73 \text{ m}^2$
  - e. SGOT, SGPT  $\leq 2.5 \times \text{ULN}$  if no liver metastasis present; SGOT, SGPT  $\leq 4 \times \text{ULN}$  if liver metastasis present
  - f. Albumin  $\geq 2.0 \text{ g/dL}$
  - g. Total serum bilirubin  $\leq 1.5 \times \text{ULN}$  ( $\leq 3 \times \text{ULN}$  or direct bilirubin  $\leq 1.5 \times \text{ULN}$  if known Gilbert's syndrome)
  - h. Potassium within institutional normal limits
  - i. Phosphorus  $\leq$  institutional upper limit of normal

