## 6. STUDY CALENDAR

Parameter	Pre-Study 	Month/Week/Cycle				End of Treatment 	28 Day Follow-up 	Long Term Follow-up 
		D1, 8, 15 and 22 Cycle 1	D1 and 15 Cycle2	D1 of every Cycle 	Every 8 weeks			
Demographics	X							
CLINICAL EVALUATIONS:								
History and Physical	X	X	X	X		X		
Toxicity Assessments	X	X	X	X		X	X	
Concomitant Medications Assessments	X	X	X	X		X		
Height	X							
Vital Signs and Weight	X	X	X	X		X		
Performance Status	X	X	X	X		X		
Ophthalmologic Exam	X 							
Amsler Grid Test 				X		X		
LABORATORY/RADIOLOGIC EVALUATIONS:								
Hematology (CBC/diff, PLT)	X	X	X	X		X		
Comprehensive Metabolic Panel 	X	X	X	X		X		
Magnesium	X	X	X	X		X		
Phosphorus	X	X	X	X		X		
Parathyroid Hormone (PTH)		X 	X					
Total vitamin D		X 	X					
EKG	X							
Tumor Evaluation 	X				X			
TREATMENT ADMINISTRATION:								
Erdafitinib		Daily						
Palbociclib		Days 1 - 21 of every 28-days cycle						
Fulvestrant		X 		X				
Pill Diary 				X				

Meal Record		X 	X					
CORRELATIVE STUDIES:								
Tumor Tissue Collection 	X							
Blood Collection needed to accompany tissue for NGS analysis 	X							
FGFR1 FISH Analysis	X							
Blood Collection for cfDNA 	X				X	X		
Blood Collection for Pharmacokinetic Assessments		X 	X					
Blood Collection for Pharmacodynamic Assessments		X 	X					
FOLLOW-UP:								
Chart review for progression status 								X

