## 7.6 Concomitant Treatment and Supportive Care Guidelines

Because there is a potential for interaction of erdafitinib and palbociclib with other concomitantly administered drugs through the cytochrome P450 system, the case report form must capture the concurrent use of all other drugs, over-the-counter medications, or alternative therapies. The Protocol Chair should be alerted if the patient is taking any agent known to affect or with the potential to affect selected P450 isoenzymes (Cautionary Concomitant Medications list). Patients taking any of the medications on the Cautionary Concomitant Medications list are encouraged to seek alternative medications; if not possible, patient will not necessarily be excluded from entering the study, but approval by the Study Chair has to be obtained prior to enrollment. Patients already enrolled in the study that initiate and persist taking any of the medications on the Cautionary Concomitant Medications list will also require approval from the Study Chair.

Patients on chronic medications that can be given concomitantly with erdafitinib and palbociclib should be maintained on the same dose and dose schedule throughout the study period, as medically feasible. The investigator should instruct the patient to notify the study site about any new medications he/she takes after the start of the study drug. All medications (other than study drug) and significant non-drug therapies (including physical therapy and blood transfusions) administered after the patient starts treatment with study drug, and any changes in dosing should be recorded.

All supportive measures consistent with optimal patient care can be given throughout the study at the discretion of the treating physician, as long as they are not part of the list of prohibited medications. In general, the use of any concomitant medication/therapies deemed necessary for the care of the patient is permitted with the following considerations:

- Prophylactic anti-emetics should be started only once the patient experienced nausea or vomiting at the discretion of the investigator.

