#### Metabolism

To date, pharmacokinetic data have been collected in 4 clinical studies for a total of 138 cancer patients. The exposure and Cmax increased in a dose-proportional manner over the range of 25 to 225 mg once daily (QD) following palbociclib administration on days 1 and 8 of cycle 1, although some low to moderate variability around these doses was observed, particularly at the 150 mg QD dose level. Following repeated daily dosing to day 15 and day 21 (assumed to be steady state), palbociclib was absorbed with a median Tmax of ~4 h. The mean palbociclib Vz/F was 3103 L, which is significantly greater than total body water (42 L), indicating that palbociclib extensively penetrates into peripheral tissues. Palbociclib was eliminated slowly; the mean t1/2 was 26.5 h (range 15.8 to 36.2 h) and the mean CL/F was 86.1 L/h. Palbociclib accumulated following repeated dosing with a median Rac of 2.4, which is consistent with a half-life of ~27 h. Preliminary results from the recently performed food effect study (A5481021) suggested that the administration of palbociclib with food results in more consistent drug absorption and exposure than administration of palbociclib in a fasted state. As a result of these findings, patients should be instructed to take palbociclib with food. CYP3A4 inhibitors/ inducers should be avoided.

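### Strong CYP3A inhibitors and inducers may be taken in Cycle 1 on Study Chair approval, with no palbociclib action and no DLT-evaluability rule for the patients who take them

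*Combined protocol and SAP*

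**What the plan says.** **Permission.** The Synopsis inclusion criteria state: "Current use of any of the drugs listed on the Cautionary Concomitant Medications list has to be approved by the Study Chair". Section 4.1.9 repeats it: "Current use of any of the drugs listed on the Cautionary Concomitant Med list has to be approved by the Study Chair". Section 7.6 asks patients to look for another drug first and otherwise requires approval before enrollment. It applies the approval requirement also to "Patients already enrolled in the study that initiate and persist taking any of the medications on the Cautionary Concomitant Medications list". None of these places treats Cycle 1 differently.

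**The list.** Section 19 puts moderate and strong CYP3A4 agents under joint headings without marking which are strong. Itraconazole, ketoconazole, clarithromycin, rifampin, phenytoin and carbamazepine are all there. Its instruction to seek alternatives mentions erdafitinib only.

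**Palbociclib.** Section 9.3 (Metabolism) says "CYP3A4 inhibitors/ inducers should be avoided". Section 3.2.1 reports: "The strong CYP3A inhibitor itraconazole increased palbociclib AUC" by about 87%, and "coadministration of rifampin, a strong CYP3A inducer, decreased palbociclib AUC" by 85%. On the phase I experience it says: "Other than neutropenia, which was proportionate to drug exposure", palbociclib was well tolerated.

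**Other controls.** The Study Calendar (Section 6) schedules blood counts at "D1, 8, 15 and 22 Cycle 1". Section 8.4 gives holds and reductions by toxicity grade. Section 9.1 adds close monitoring, with interruption of erdafitinib as the named action. Section 10.6 samples erdafitinib and palbociclib PK in all escalation patients on Days 1 and 15 of Cycles 1 and 2. Section 7.4 makes a patient evaluable for DLT on receipt of at least 75% of study drug, and Section 7.5 forbids escalation within a patient.

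**The concern.** Every dose level starts palbociclib at 125 mg, and only erdafitinib varies, so DLT counts are read as information about erdafitinib. That reading assumes palbociclib exposure is roughly the same from patient to patient. An approved strong inhibitor nearly doubles it, and an approved strong inducer removes most of it.

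Two things are at stake. The first is safety. The protocol links neutropenia to palbociclib exposure, yet nothing tells the site to start lower or hold palbociclib when an inhibitor is approved. The second is interpretation. Grade 4 ANC is a DLT (Section 7.4), so an inhibitor can add one that erdafitinib did not cause. An inducer can yield a clean cycle that says little about the triple combination. No document gives a criterion for approval, a palbociclib action, or a rule for how such a patient enters the dose decision.

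**Working it through.** No sample size, power or error rate in the plan depends on this point. The check covers exposure, evaluability and the 3-patient decision.

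**1. Exposure.** Inputs: 125 mg start (Section 7.3.2); AUC ratios 1 + 0.87 = 1.87 and 1 − 0.85 = 0.15 (Sections 3.2.1 and 9.3). Dose-equivalent = dose × ratio.
- With itraconazole: 125 × 1.87 = 233.8 mg.
- With rifampin: 125 × 0.15 = 18.8 mg.
- After one reduction with itraconazole: 100 × 1.87 = 187.0 mg.
- After two: 75 × 1.87 = 140.3 mg, and 140.3/125 = 1.12.

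Section 9.3 gives dose-proportionality from 25 to 225 mg, so the first two are approximate. Two reductions nearly correct over-exposure, but the specified trigger for them is toxicity.

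**2. Effect on a cohort.** Mean palbociclib AUC relative to a cohort with no such patient, when one patient is affected:
- Cohort of 3: (1 + 1 + 1.87)/3 = 1.29; (1 + 1 + 0.15)/3 = 0.72.
- Six patients: (5 + 1.87)/6 = 1.145; (5 + 0.15)/6 = 0.858.

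**3. Evaluability.** The rule asks for 75% of drug received. A patient on rifampin who takes every dose meets it at about 15% of usual palbociclib exposure. There is no toxicity to prompt a change, and the dose cannot be raised.

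**4. The 3-patient decision.** Section 17.2.1 says in words that 0/3 is escalate (E), 1/3 is stay (S) and 3/3 is de-escalate and exclude the dose (DU). For 2/3 the text copy of Table 17.2.1 needs care, because blank cells for impossible outcomes have dropped out and entries have shifted left. I recomputed mTPI with the stated target 0.20 ± 0.05, assuming a Beta(1,1) prior and a 0.95 exclusion cutoff, neither of which is stated. This returns all three worded examples. For the other cells that matter:
- 2/3: posterior Beta(3,2); P(p > 0.20) = 1 − (4 × 0.2³ − 3 × 0.2⁴) = 1 − 0.0272 = 0.973 > 0.95, so DU. Row 2 of the table, realigned to start at 2 patients, also reads DU here.
- 3/6: posterior Beta(4,4); P(p > 0.20) = 1 − P(Bin(7, 0.2) ≥ 4) = 1 − 0.033 = 0.967 > 0.95, so DU.
- 1/6 and 2/6: S.

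In a cohort of 3, one added or missing DLT therefore moves the decision between E and S, or between S and DU. At 6 patients there is more slack: 1 and 2 DLTs both give S.

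**5. Illustration with assumed DLT rates.** Let p be the DLT risk of unaffected patients.
- One of three under-exposed with risk 0: P(0/3) goes from (1 − p)³ to (1 − p)². For p = 0.1, 0.2, 0.3 that is 0.73 to 0.81, 0.51 to 0.64, and 0.34 to 0.49.
- One of three over-exposed with risk 0.50: P(at least 2/3) goes from 3p² − 2p³ to p² + 2p(1 − p) × 0.5. For the same p that is 0.03 to 0.10, 0.10 to 0.20, and 0.22 to 0.30.

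The risks of 0 and 0.50 are mine. Section 8.3.1 reports no Grade 4 neutropenia in Cycle 1 among 22 patients on palbociclib 125 mg alone (exact 95% upper limit 1 − 0.025^(1/22) = 0.154). No rate at raised exposure is given.

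**The case against.** A reader might infer that the existing controls act only after toxicity, or that nothing covers inducers. The documents do not support either. Section 7.6 is triggered by the co-medication itself: alert the Protocol Chair, seek alternatives, obtain approval. Sections 9.1 and 19 also ask for alternatives, and Section 19 lists the inducers. Palbociclib PK is drawn in Cycle 1 from every escalation patient, and Section 14.3 sets teleconferences every other week during escalation. A careful Study Chair could prevent most of the problem.

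Nor is this a flat contradiction. Section 7.6 names palbociclib, and the advice in 9.3 to avoid these drugs can be read as consistent with seeking alternatives first. Choosing a bar over case-by-case approval is a judgement about strictness.

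It is also tempting to say that full-dose palbociclib resumes after a Grade 3 ANC that resolves within 7 days. Section 8.4 says so, but Sections 7.5 and 17.2.1 require reduction for Grade 3 or 4 toxicity. The documents conflict, so the point should not rest on it.

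The size is a worst case. No AUC effect is given for other listed drugs. Section 4.2.9b screens out many anti-infectives at entry, though not later, and does not touch anticonvulsants such as phenytoin or carbamazepine. Severe neutropenia is common without any interaction: Section 3.2.1 gives 62.0% Grade 3 or 4 with palbociclib plus fulvestrant (not limited to Cycle 1), so a neutropenic DLT could not be pinned on the inhibitor with confidence.

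What the objection leaves in place: approval has no stated criterion, and the only named interaction action concerns erdafitinib. PK samples are shipped in batches (Section 10.1), and Section 10.6 links PK to new cohorts or schedules, not to an individual's dose or evaluability.

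**Conclusion.** The point holds as a gap in the rules. Followed as written, the protocol can place a patient at about 1.87 or 0.15 times usual palbociclib exposure inside a 3-patient erdafitinib decision. It states no palbociclib action and treats the patient as ordinary for evaluability. One such outcome can turn escalate into stay, or stay into permanent exclusion of a dose level, and the reverse for an under-exposed patient.

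This rests on the protocol's AUC figures for one inhibitor and one inducer, approximate dose-proportionality, and, for 2/3 and 3/6, the assumed prior and cutoff. The number of affected patients is unknown. A reader might infer that the MTD will be biased or that the mTPI operating characteristics are compromised; without a frequency or DLT rates at altered exposure, the documents cannot support that. This is a cheap improvement to safety and interpretability, not a defect that undermines the design.

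**What to change.** 1. In Sections 4.1.9, 7.6 and 19 (and the Synopsis), mark which CYP3A agents are strong and name palbociclib as well as erdafitinib.
2. Do not permit strong inhibitors or inducers at entry or through the 4-week DLT window, for escalation and expansion patients. Preferably extend this through the 8-week tolerability window of Section 17.2.1, since the phase II dose depends on it. Require a washout suited to the drug. The 14-day stop in Section 7.6 is for herbal preparations and is no basis for withdrawing, for example, an anticonvulsant.
3. Keep Study Chair approval for moderate agents and for later use.
4. If a strong inhibitor becomes unavoidable, state a palbociclib action (hold or reduce). If the 75% rule is read as palbociclib doses, 0.75 × 21 = 15.75, so a hold of up to 5 of 21 doses leaves the patient evaluable.
5. If a strong modulator is nevertheless taken in Cycle 1, keep any DLT in the mTPI count, flag the case at the dose decision, and show PK summaries with and without that patient. A flag does not undo a misleading clean cycle; the bar in item 2 is the real protection.

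Cost: protocol wording and one extra PK listing. Downside: a few patients who cannot change drugs become ineligible, in a number the documents do not allow one to estimate.
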